#### **8.1.3 Packaging, Labelling and Supply (re-supply)**

The IMD is labelled by printing the name of the device directly onto the device. There is an individual serial number that also printed on the device. The production batch can be tracked through this serial number. The hearing aids are shipped in a box with a label on the outside of the box that states the family name of the product, the serial number, a short description (colour and performance level), and an expiration date. Inside the box is a case that houses the hearing aids. The hearing aids are delivered inside a blister inside of this case. The HCP removes the case from the box and removes the hearing aids from the blister. The case is generally given to the end user in which to place the hearing aids whenever they are not worn.

#### **8.1.4 Storage Conditions**

The IMD devices are shipped from production when they are ordered. The conditions in which they should be shipped and kept by the end user are described in the IFU. They should not be exposed to temperatures below -25° and not above 60° Celsius.

### **8.2 Administration of experimental and control interventions**

#### **8.2.1 Experimental Intervention**

The IMD is worn over the ear with the speaker covered by a dome or earmold anchored inside the ear canal. It is non-invasive. The amplification is prescribed based on the participant's hearing loss. The IMD will be worn by each participant for 10 +/- 7 days to give the subjects enough time to get used to the amplification and then a further 10 +/- 7 days to wear the devices in different environments and make a comparison between the IP and the SP. Normal use of a hearing aid is 8-10 hours per day. The participants will be instructed to use the IP for the same amount of time as the SP in music situations. The hours of daily use will be controlled with a data logging feature in the software that programs the hearing aids.

The study procedure will use a randomized single-arm design in which all of the subjects will wear the IMD programmed with both the IP and the SP. As stated previously, the device is non-invasive and requires no surgical procedure.

The subjects themselves will place the device in their ears each morning and remove them each night for sleeping. They will also be responsible for switching between the IP and SP programs to use both and compare them in music situations. It is expected that some of the test subjects will be experienced hearing aid users and some will be new users. However, they will require minimal explanation and/or training to use the IMD. They will be given an Instructions for Use booklet that explains how to insert the device and provides further instructions concerning cleaning, battery charging, and warnings.

## 8.2.2 Control Intervention

There is no RMD. The control intervention is the SP and will be programmed into the IMD.

## 8.3 Dose / Device modifications

The IMD will provide the amplification prescribed by the fitting rationale and will be measured with Real Ear Measures (REM). The SP and the IP will be programmed with the P1 gain as a reference with fine-tuning performed on the IP. Because the gain will be verified objectively and fine-tuned based on the patient's comments, it is not expected that any negative effects should be experienced that would make them want to discontinue use of the device. However, if a subject does report such differences, it will be possible to improve the programming with fine tuning. Fine tuning can improve the situation by making slight changes to the gain (higher or softer) enough for the subject to continue with the study. If the subject requests to discontinue they can immediately remove the IMD from their ear(s) and do not need to wait until their next appointment in order to do so. They will be asked to return the IMD to Bernafon AG, but their data will still be included in the results for the current study. All data will remain encoded because the results are only recorded using the identification code of the subject.

## 8.4 Compliance with study intervention

It is clearly explained to the subjects that during the intervention period it is important to the study that they only wear the IMD (in the case of current users with their own hearing aids). The importance of switching between the IP and SP during music situations is also explained. Additionally, they will receive an email as a reminder to use both programs during the field test. For current hearing aid users, their own hearing aids are left in their possession for safety reasons in the event that they choose to discontinue their participation in the trial, or a problem arises with the test devices. For ethical purposes, the subjects must have a back-up solution for their hearing impairment.

The data logging feature of the software monitors the average number of hours that the devices are worn each day and in each program. Therefore, it will be noted if the IP and the SP have not been worn a standard or expected amount of time.

## 8.5 Data Collection and Follow-up for withdrawn participants

Any data that is collected will be kept in the Smart Trial data management database. The data will remain encoded because results are only recorded using the identification code of the subject. The analysis and report will include a summarized section based on the data available from all recruited subjects and another section based on the data from the subjects that complete the entire protocol. Withdrawn subjects will have the same follow-up as those subjects that complete the trial. Those subjects that are taken from the Bernafon directory, including those that withdraw, are welcome to return to the clinic for fine-tuning and maintenance as needed.

## 8.6 Trial specific preventive measures

The performance of a hearing aid is not impacted by medication or other conditions. The subjects will continue to take whatever type of medication that they normally take. There will be no impact on the study objectives.

## 8.7 Concomitant Interventions (treatments)

Test subjects will continue to receive any concomitant care and medication that they normally receive during the trial. Some test subjects will already be hearing aid users and will have, therefore, used them while receiving other types of care or medications. There will be no impact on the study.

objectives.

### **8.8 Medical Device Accountability**

The IMD devices have serial numbers by which the individual device can be identified, and the production history traced. The devices will be shipped from the production lab in Poland. The serial numbers will provide traceability of their production. All devices undergo testing in production before being shipped. Only IMD that are from a tested batch will be used in the study.

### **8.9 Return or Destruction of Study Drug / Medical Device**

At the end of the study all of the subjects will return the IMD to the site in Bern. It will be noted in the device accountability log and CRF that the devices were returned.

The PI will then return the devices to the Sponsor.

## **9. STUDY ASSESSMENTS**

### **9.1 Study table of study procedures and assessments**

Study Periods	Screening	Treatment/Intervention Period	
Visit	1	2	3
Day	0	10 +/- 7 days	20 +/- 7 days
Patient Information and Informed Consent	x		
Demographics	x		
Medical History	x		
In-/Exclusion Criteria	x		
Otoscopy	x	x	x
Audiometry	x		
Randomisation of treatment	x		
Administer Medical Device	x		
REM	x		
Optimized fitting		x	
Primary Variable (Preference questionnaire)			x
Secondary Variable (Lab test-music perception)	x	x	x
Other Variables (Product questionnaire)	x		
Other Variables (Music perception questionnaire)	x	x	
Adverse Events	x	x	x

## 9.2 Assessments of outcomes

### 9.2.1 Assessment of primary outcome

The primary outcome is the preference questionnaire. The hearing aids will be programmed with the two music programs, the SP with the standard default music settings and the IP with the optimized fine-tuned music settings. The subjects will use both programs during the second field test and then be asked to choose a preference for listening to music and/or when playing music. The questionnaire also asks that they rate how sure they are of their choice on a 10-point scale with 10 being completely sure and gives a list of reasons for the choice from which they can select as many as they choose.

### 9.2.2 Assessment of secondary outcomes

The Adaptive Music Perception (AMP) test will be run in the lab. The test is designed to assess aspects of music including meter and timber. The test is a computerized two-alternative forced-choice method run on a touch screen. The adaptation process uses a two-down, one-up rule and the score is the average of the last four reversal points. A reversal point is when the subject makes a correct selection and the adaptation reverses to a lower level.

They will also complete a product questionnaire with specific questions about feedback, sound quality, and unexpected behaviour for the general P1 program. The questionnaire is given to them to take home at the first appointment to be filled out and returned at the second appointment. The questions are rated with either a 5-point scale with 1 being the most positive outcome or yes/no answers. They will complete a music perception questionnaire for all three programs. The questions are rated with a visual analogue scale (VAS). The music questionnaire for P1 will be given to them at the first appointment and returned at the second. The music questionnaires for P2 and P3 will be given to them at the second appointment and returned at the third.

### 9.2.3 Assessment of safety outcomes

Questions concerning unexpected events, sounds, and behaviour are included in the product questionnaire that are given to them to take home at the first appointment to be filled out and returned at the second appointment. The questions are rated with yes/no answers.

In addition to the questionnaires, adverse events will be collected and monitored.

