### **3.6 Explanation for choice of comparator**

The comparator program will be the current standard default music program (SP) available in the fitting software. The hearing aids are always fit with an initial program (P1) that is a general program to be used in most situations. The default music program (SP) is an optional additional program that offers a range of 1-4 dB of more gain (in reference to the general program) at specific frequencies to enhance music. The test participants will be fit with the devices with both the SP and the IP as a second and third program (randomized) to make a side by side comparison of the programs in various music situations.

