### **4.4 Safety Objectives**

The study aims to assess the overall safety of the IMD by testing for unexpected behaviour from the IMD and by the collection of AEs to identify any new risk factors since their release to the market.

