### 5.2 Secondary Outcomes

Secondary outcomes will be measured with an adaptive music perception test (AMP) developed by Kirchberger and Russo (2015). The test uses recordings and asks the subjects to judge different aspects of music such as meter and timbre. The overall sound quality and benefit of the hearing aids in daily life will be measured with product questionnaires. The product questionnaire for the general P1 will be used to control for a general acceptance of the hearing aids and will be answered one time after the first field period. The music perception questionnaire will be used to judge sound quality of music and will be answered three times, one for each hearing aid program. The music questionnaire will be answered for P1 at the end of the first field test and for P2 and P3 at the end of the second field test.

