### **6.1.3 Other methods of minimising bias**

The IMD will be programmed with a P1 to be used in general listening situations. All test subjects will wear the hearing aids for the first field test of 10 +/- 7 days with this program to become accustomed to the amplification. They will continue to use P1 during the second field test with the SP and IP added as the second and third programs. P1 will serve as a control in the circumstance that the subject's rate both the music programs poorly, to determine whether only the music programs are the problem or whether they have not accepted the device overall.

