#### **9.3.2 Fitting/Second visit**

Fitting Visit, Day 10 +/- 7: Otoscopy is performed, and the subjects return the completed questionnaires. The IMDs are fitted with IP and SP as specified by the randomization carried out at the first visit. The IP is optimized and fine-tuned based on comments that the subject makes about the sound while they play their instrument in the clinic. The SP is programmed without any adjustment based on the default music program offered in the software. They are instructed to switch between programs two and three when playing and listening to music for the next 10 +/- 7 days. They perform the lab test with the AMP in one condition: aided with P2. The subjects are given the music perception questionnaires and instructed to complete them at home a day before their next appointment. One questionnaire pertains to P2 and the other to P3. Any AEs are reported in the CRF. They are scheduled for the third visit.

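### The structured device-behaviour questions are planned once, for P1, before either music program is loaded; Protocol 9.3.3 conflicts with this, and SAP 6.2.4 compares conditions that are not collected

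*Protocol*

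**What the plan says.** - **Objective.** Protocol 4.4: "The study aims to assess the overall safety of the IMD by testing for unexpected behaviour from the IMD", together with adverse event (AE) collection. Section 5.3 defines unexpected behaviour as feedback or whistling, distortion or artefacts, muting or shut-off, and unexplained signals or loud sounds.
- **Instrument and timing.** Protocol 9.2.3: "Questions concerning unexpected events, sounds, and behaviour are included in the product questionnaire that are given to them to take home at the first appointment", with return at the second. Section 9.2.2 fixes the program: "They will also complete a product questionnaire with specific questions about feedback, sound quality, and unexpected behaviour for the general P1 program". Section 5.2 says this form "will be answered one time after the first field period". SAP 6.2.4 uses its results to judge the safety of the device.
- **When the music programs arrive.** Protocol 9.3.2 (visit 2): "The IMDs are fitted with IP and SP as specified by the randomization carried out at the first visit". The forms then handed out are music perception questionnaires: "One questionnaire pertains to P2 and the other to P3".
- **Conflicting text.** Protocol 9.3.3 has participants return completed product questionnaires at visit 3. Section 5.3 speaks of questionnaires, in the plural, as carrying the safety questions.
- **P1 as control.** Protocol 6.1.3: "P1 will serve as a control in the circumstance that the subject's rate both the music programs poorly".
- **Analysis.** SAP 6.2.4 plans a Wilcoxon signed-rank test between conditions on the feedback and sound-quality items of the general (product) questionnaire.

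**The concern.** The form designated for unexpected device behaviour is returned at the visit where the two programs under comparison are first loaded. A clean result on it would describe P1 during the run-in. The second field period differs in ways that bear on sound output. SP "offers a range of 1-4 dB of more gain (in reference to the general program") at specific frequencies, and IP is retuned individually while the participant plays. Protocol 3.1 itself names distortion and acoustic feedback as problems when music is amplified.

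Two further consequences follow from the single administration. The signed-rank test in SAP 6.2.4 has nothing to pair. And 6.1.3 relies on P1 to separate poor music programs from non-acceptance of the device, yet P1 is rated after period 1 and the music programs after period 2, so that comparison is mixed with period and acclimatisation.

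**Working it through.** The plan states no safety precision or event rate to reproduce. The 18-20 participants come from published sample sizes and recruitment prospects (Protocol 11.2, SAP 3.3). The check is therefore a cross-reading and a count.

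**1. Issue and return of forms**

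| Form | Program | Issued | Returned | Source |
|---|---|---|---|---|
| Product | P1 | Visit 1 | Visit 2 | 5.2, 9.2.2, 9.2.3, 9.3.1 |
| Music | P1 | Visit 1 | Visit 2 | 9.2.2, 9.3.1 |
| Music | P2 and P3 | Visit 2 | Visit 3 | 9.2.2, 9.3.2 |
| Product | not stated | no issue described | Visit 3 | 9.3.3 |

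Both schedule tables mark the product form at visit 1 only and the music form at visits 1 and 2. Those are hand-out visits, so a second product form would need a mark at visit 2, and there is none. Section 9.3.3 also mentions no music questionnaires, although 9.3.2 makes those the forms due back at visit 3. The likeliest reading is that 9.3.3 names the wrong form, but the text does not settle it.

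**2. Planned responses, taking the first three rows**

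- Product form per participant: P1 1, IP 0, SP 0. Over 18-20 participants: P1 18-20, IP 0, SP 0.
- P1 questionnaire ratings in the second field period: 0.
- AE enquiries after IP and SP use: 1 (visit 3; Protocol 9.2.3.1 and 10.1).
- Artifact ratings on a visual analogue scale after period 2: 1 for IP and 1 for SP (SAP 6.1.4).

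**3. Field time covered by the product form**

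Each period is 10 +/- 7 days, that is 3 to 17.

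- Nominal: 10 / (10 + 10) = 50%.
- Extremes: 3 / (3 + 17) = 15% and 17 / (17 + 3) = 85%.

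In every case, none of the covered days has IP or SP loaded.

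**4. The test in SAP 6.2.4**

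A signed-rank test needs two values per participant. One administration for one program gives one value, hence no differences to rank.

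**5. What asking by program would yield**

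There would be 18-20 responses for each program. The chance of at least one yes is 1 - (1 - p)^n, with p assumed because the documents give no rate:

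- p = 5%: 1 - 0.95^18 = 60%; 1 - 0.95^20 = 64%.
- p = 10%: 1 - 0.90^18 = 85%; 1 - 0.90^20 = 88%.

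As planned, these items can yield no yes for IP or SP at any p.

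The one-sided 95% upper bound after zero events, 1 - 0.05^(1/n), is 15.3% for n = 18 and 13.9% for n = 20. It reflects only the sample size and would be the same for each program after the fix, so it does not measure this gap.

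**The case against.** A reader might infer that safety is not systematically assessed under IP and SP. The documents do not support that. AEs are solicited from every participant before the end of each appointment, including visit 3. Device deficiencies, defined to include malfunction, are collected throughout (10.1) and source-verified for all patients (12.3). The music questionnaire rates artifacts for both programs, and artefacts are among the behaviours named in 5.3. The objective is also stated for the device, not for each program. All of this stands. What remains is narrower. The examples that 9.2.3.1 gives participants are medical, no attribution of events to a program is described, and nothing listed for period 2 asks about feedback, muting, shut-off or warning signals.

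A reader might also infer that P1 cannot serve as a control. That goes too far. SAP 3.1 deliberately makes first-field-test data each participant's reference, a first-period rating does bear on acceptance of the device, and wear time is logged by program (Protocol 8.4), which shows whether P1 stays in use. The comparison is weakened by confounding with period, not lost. The IP versus SP comparison is unaffected, since both are rated in the same period.

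That the second period is the likelier setting for feedback or distortion is a plausible inference but not a documented figure; Protocol 8.3 allows fine tuning to lower gain as well as raise it.

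The strongest counter-argument is 9.3.3. Taken literally, with the plural in 5.3 and the between-conditions test in SAP 6.2.4, it would mean a second administration was intended. If so, the gap lies in 5.2, 9.2.2, 9.2.3, 9.3.2 and the schedules instead. Either way the sections cannot all be right.

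**Conclusion.** The point holds in a limited form. As most of the text reads, the structured device-behaviour items have 18-20 planned responses for P1 and none for IP or SP. Second-period safety then rests on a solicited but not program-attributed AE enquiry, device-deficiency collection and one artifact rating per music program. The test in SAP 6.2.4 cannot be run on one condition. P1's control role is weakened by confounding with period and acclimatisation.

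This rests on two assumptions: that 9.3.3 names the wrong form, and that the music questionnaire contains no device-behaviour items beyond the content summarised in SAP 6.1.4. The questionnaires are an appendix that is not in the material reviewed. If either assumption fails, the gap in coverage narrows or closes, but the contradiction with 9.3.3 still has to be resolved. The change is worth making mainly because it is cheap and lets the trial assess its own safety outcome under the programs it compares.

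**What to change.** - Issue the existing product questionnaire again at visit 2 for return at visit 3, with the feedback, sound-quality and unexpected-behaviour items answered separately for P1, P2 and P3. Asking by slot number keeps participants blinded; the statistician maps slots to IP and SP from the randomization list.
- The P1 answers then also give a rating from the same period as the music programs, for use under 6.1.3.
- Tabulate the safety answers by program.
- Reconcile Protocol 5.2, 5.3, 9.2.2, 9.2.3, 9.3.2, 9.3.3 and both schedule tables on which form is issued and returned when.
- In SAP 6.2.4, name the conditions compared (for example IP versus SP in the second period) or drop the test and describe the answers.

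Cost: one more short form per participant, completed at home, and an amendment to the schedule and eCRF. No extra visit is needed.

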#### 9.2.3.1 Adverse events

For the recording of adverse events the subjects will be asked for a description of the event including time/date of onset, how long it lasted, how many times it occurred, and if it caused discomfort or pain or a disruption of hearing ability.

Before the end of each appointment, the subjects will be asked if they have experienced any adverse events. It will be explained that adverse events are not restricted to problems related to the hearing aids or their hearing but can include allergies, broken legs, headaches, etc. They will be recorded on the AE forms in the CRF.

#### 9.2.3.2 Laboratory parameters

Not applicable

#### 9.2.3.3 Vital signs

Not applicable

### 9.2.4 Assessments in participants who prematurely stop the study

After the study concludes the subjects will return the IMD. The follow-up procedure will be the same as for all active test subjects. They will be instructed to return to the clinic for any required maintenance or fine-tuning of their own devices. Those that prematurely withdraw from the study will

still be wearing their own devices; therefore, their follow-up treatment will be the same as for the other participants that finish the study.

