#### **9.3.3 Lab/Third visit**

Final Visit, Day 20 +/- 7: Otoscopy is performed. The subjects return the completed product questionnaires. They perform the lab test with the AMP in one condition: aided with P3. They complete a preference questionnaire during the appointment. They are notified that the trial has ended and those that normally wear hearing aids can return to using their own devices. They will return the IMD to the clinic. Any AEs are reported in the CRF. Those that are on the Bernafon subject list and normally wear devices fitted by the Bernafon clinic are reminded to return to the clinic for normal maintenance of their hearing aids. Anyone that would like to join the Bernafon clinic are also welcome to do so.

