- The effect of the instrument, i.e. the sound generation principle greatly varies between a string, a woodwind and a brass instrument. This might affect the perception of sound and interact with the range of the instrument, the hearing loss degree and type,
- The effect of amplification through hearing aids when musicians are playing. All the above-mentioned tests are based on passive listening experience. There are no publications, to the best of our knowledge, about the use of auditory feedback to control the production of music. We can assume that adaptation of their own voice production to the environment (Lombard effect) and perception of sound might show similarities when playing music,
- The effect of the IP which follows guidelines for hearing aids fitted to musicians. The guidelines are based on a project (Greasley et al., 2019) but no results based on quantitative research were published. It is therefore not possible to estimate an effect size when a personalized protocol like the IP is used with musicians.

The uncertainty from the test design and the unknown effect size from the IP motivates the choice for a larger sample size. Regarding recruitment possibilities, based on the principal investigator's input, the sample size was set to 18-20 participants for the current study.

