### **11.4 Planned Analyses**

#### **11.4.1 Datasets to be analysed, analysis populations**

Primary analysis of the primary outcome will be based on the intention-to-treat (ITT). The ITT population will include all participants with associated primary outcome data, excluding only subjects who were deemed ineligible following the screening visit, those who withdrew from the trial and were unwilling for their previously collected data to be utilised or those who failed to provide baseline.

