#### **11.5 Handling of missing data and drop-outs**

Unless specified otherwise in each objective, no statistical techniques will be used to impute missing data. If a subject's data are missing for any reason, that subject will not be included in that portion of the analysis. The number of subjects included in each analysis will be reported so that the potential impact of missing data can be assessed.

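### The preference question is asked only at visit 3, so a participant who tries both music programs and then stops has no primary outcome and leaves the primary analysis

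*Protocol*

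**What the plan says.** **Collection.** The schedule of assessments (Protocol 9.1) marks the preference questionnaire at visit 3 only. Section 9.3.3 places it inside that visit: "They complete a preference questionnaire during the appointment". The music questionnaires for the second and third program slots go home with the participant at visit 2 (9.3.2). The preference questionnaire does not.

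**Stopping.** A participant may withdraw at any time without giving a reason (7.4), and may take the device off without waiting for the next appointment (8.3). Those who stop are asked to return it.

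**After stopping.** Section 9.2.4 mentions device return and then care of the participant's own aids: "They will be instructed to return to the clinic for any required maintenance or fine-tuning of their own devices". Section 8.5 says: "Withdrawn subjects will have the same follow-up as those subjects that complete the trial". The only content it gives to that follow-up is fine-tuning and maintenance in the clinic.

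**Analysis.** Protocol 11.4.1: "The ITT population will include all participants with associated primary outcome data". Protocol 11.5 imputes nothing unless an objective says otherwise: "If a subject's data are missing for any reason, that subject will not be included in that portion of the analysis". SAP 6.3 has the same rule.

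**Data of those who stop.** The statements differ:
- Section 7.4 says data gathered from withdrawn participants will be used. Section 8.3 says of those who stop, "but their data will still be included in the results for the current study".
- Section 8.5 plans one report section on data available from all recruited participants and another on completers.
- Section 10.1, on withdrawal for pain, gives removal of partial data as one purpose.
- SAP 4.2, read literally, excludes everyone who withdrew. Protocol 11.4.1 excludes only those who withdrew and refused use of their data.

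**The concern.** The primary outcome exists only for people who reach visit 3. In the second field period the new element is the pair of music programs, and 8.3 itself discusses discontinuation alongside unwelcome effects of the programmed gain. Stopping in that period may therefore be related to what the preference question measures. If it is, the primary result describes those who finished and not those who tried both programs.

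Section 7.4 keeps at least five screened back-up participants to replace withdrawals. The analysed number can then stay at the planned size while preferences are being lost, so a count of subjects analysed would not reveal it.

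**Working it through.** **1. The plan's own figure.** There is no power calculation to reproduce. Protocol 11.2 cites earlier samples of 9 to 21, and "the sample size was set to 18-20 participants for the current study" on recruitment grounds. It adds: "It is therefore not possible to estimate an effect size when a personalized protocol like the IP is used with musicians". No drop-out rate is given. The number of stoppers and their preferences below are therefore assumptions.

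**2. Test.** The plan uses a Wilcoxon signed-rank test on a five-point preference score (Protocol 11.4.2), two-sided at 0.05 (SAP 4.1). If every score is one step from the middle, all ranks tie and the exact test equals the sign test. With k of n preferring IP (k > n/2):

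p = 2 × [C(n,k) + C(n,k+1) + … + C(n,n)] / 2^n

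Example, 13 of 17: 2 × (2380 + 680 + 136 + 17 + 1) / 131072 = 6428 / 131072 = 0.049.

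**3. Worst case.** Completers have the smallest IP count that reaches p ≤ 0.05, and every omitted stopper prefers SP.

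| Enrolled | Stoppers | Completers for IP | p | With stoppers counted | p |
|---|---|---|---|---|---|
| 18 | 1 | 13 of 17 | 0.049 | 13 of 18 | 0.096 |
| 20 | 1 | 15 of 19 | 0.019 | 15 of 20 | 0.041 |
| 20 | 2 | 14 of 18 | 0.031 | 14 of 20 | 0.115 |
| 20 | 3 | 13 of 17 | 0.049 | 13 of 20 | 0.263 |

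**4. Replacement.** Suppose back-ups restore 20 completers, split 15 to 5 (p = 0.041). One replaced stopper who preferred SP makes it 15 of 21: 2 × (54264 + 20349 + 5985 + 1330 + 210 + 21 + 1) / 2097152 = 164320 / 2097152 = 0.078. Replacement restores the count but not the missing answer.

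**5. Other directions, using the full scale.** Take an invented pattern for 18 completers: 5 *IP much better*, 7 *IP better*, 2 *no difference*, 3 *SP better*, 1 *SP much better*. The exact signed-rank test with zeros dropped gives p = 0.052. Adding two stoppers gives:
- both *SP better*: 0.107
- both *SP much better*: 0.282
- both *no difference*: 0.052 (unchanged)
- both *IP better*: 0.026

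The omitted answers can move the result either way.

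**6. How likely is a stopper?** The chance of at least one is 1 − (1 − d)^N. For an assumed rate d of 5% to 20% it runs from 0.60 to 0.98 with N = 18, and from 0.64 to 0.99 with N = 20.

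**The case against.** **Who stops.** A reader might infer that dissatisfied users leave, so that the result is biased toward IP. The documents do not support that. General program, SP and IP sit in one device, and anyone who dislikes one can scroll to another. The first field period uses the general program alone, so trouble with the device itself can surface before the music programs are added. Section 8.3 offers fine-tuning, and 7.4 lists other reasons for withdrawal, such as an ear infection or unreliable responses. Dislike of the device as a whole need not favour either program. This stands: a link between stopping and preference is possible, but its direction is unknown.

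**Section 8.3.** A reader might also see a flat contradiction between its promise and the ITT definition. It can equally be read as covering only data already recorded, such as lab results and first-period questionnaires, and 8.5 fits that reading. There is then no contradiction, but the promise has no content for the primary outcome.

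**Silence.** No passage forbids asking a stopper for a preference, and the promised follow-up is loosely worded. True, but nothing provides for it either.

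**Weight.** The trial is exploratory, and 11.5 requires the number in each analysis to be reported. The table in the working is a worst case near the 0.05 boundary, and with one stopper among 20 its result stays below 0.05. These points limit the size of the concern. They do not remove it, because the SAP still tests this outcome at 0.05 and the reported number says nothing about what the absent participants preferred.

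**Conclusion.** The gap is real. No preference is planned for anyone who stops between visits 2 and 3, even if both music programs were used, and the analysis rules then drop that person. One to three omitted answers could change the primary result at this sample size: from p = 0.049 to 0.096 with one stopper of 18, or to 0.263 with three of 20. Those figures assume that all stoppers prefer SP, that completers only just reach significance, and that every score is one step from the middle. They show sensitivity and do not forecast a bias. The documents establish neither how many will stop, nor that those who stop are dissatisfied, nor that the omission favours IP.

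**What to change.** - **Protocol 9.2.4 and 8.5:** state that anyone who stops after visit 2 and has tried both music programs is invited, and may decline, to complete the preference questionnaire and any outstanding music questionnaires for the second and third slots. Do this when the device is asked back, in person, by phone or by post.
- **Protocol 11.4 and SAP 6.2.1:** include these answers in the ITT primary analysis, flagged as early. Report stoppers by reason where given and by which program was in which slot, and count replaced participants among them.
- **Reconcile the passages on withdrawn participants' data:** Protocol 7.4, 8.3, 8.5, 10.1 and 11.4.1, and SAP 4.2. Otherwise the literal SAP wording, or the partial-data clause in 10.1, would exclude the preferences just collected. This concerns data handling only. It leaves the withdrawal rules as they are.
- **Sensitivity analysis:** score stoppers who still have no preference against the favoured program, and name the category used, since one step and two steps gave 0.107 and 0.282 in the invented example. Scoring them as *no difference* tells nothing if zeros are dropped, and the SAP should say how zeros are handled.

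The cost is wording in two documents and a few minutes at a contact that 7.4 and 8.3 already foresee. The downside is that some preferences will rest on shorter use. That is modest, because the planned second field period of 10 +/- 7 days already allows 10 − 7 = 3 days.
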